APPENDIX C: GRADE THRESHOLDS FOR EKG

Parameter	Origin	Grades		
		1	2	3
PR interval increase (ms)*	CPI	220 to 250 and increase exceeding 20 ms	>250	Mobitz 2 or syncope
QT _c interval increase (young male) using the most accurate QT _c formula (ms)*		ULNR to 475 ms and increase exceeding 40 ms	476 to 499	>499 ms, or QTC over 460 and increase exceeding 60 ms
QT _c interval increase (women)*		Same as male plus 20 ms		

*Assuming supine position, 10 min at rest conditions, not sleeping subjects and several concordant results. ULNR, Upper limit of normal range; LLNR, Lower limit of normal range; CPI, Club phase I task force.

APPENDIX D: UNIVERSITY OF IOWA NORMAL LABORATORY VALUES

	Male	Female
Complete Blood Count		
WBC	3.7-10.5 k/mm ³	3.7-10.5 k/mm ³
Hemoglobin	13.2-17.7 g/dl	11.9-15.5 g/dl
Platelets	150-400 k/mm ³	150-400 k/mm ³
Hemogram plus Automated Differential		
Neutrophils	2188-7800/mm ³	Same
BUN	10-20 mg/dl	Same
Creatinine	0.6-1.2 mg/dl	0.5-1.0 mg/dl
Alanine Aminotransferase (ALT)	0-41 u/l	0-33 u/l
Aspartate Aminotransaminase (AST)	0-40 u/l	0-32 u/l
Chloride	95-107	Same
CO ₂	22-29 mEq/L	Same
Potassium	3.5-5.0	Same
Sodium	135-145	Same
Total Bilirubin	<=1.2 mg/dL	Same
Prothrombin Time	9-12 seconds	Same
Partial Thromboplastin Time	22-31 seconds	Same
INR	0.9-1.2	Same
Glucose (random)	<140	Same
Urinalysis, Routine Screen (using Reflectance Spectrophotometry)	Specific gravity: 1.000-1.029; pH: 5.0-9.0, Dipstick negative for protein, hemoglobin, bilirubin, urobilinogen, ketones, glucose, leukocyte esterase and nitrite	Same
Urine Microscopy	0-5 WBC, 0-2 RBC	Same
Pregnancy Test		Positive = pregnant Negative = not pregnant
Hepatitis B Surface Antigen	Negative	Same
HIV Types 1&2 Antibody	Non-Reactive	Same
Hepatitis C Virus Antibody, Version 2.0	Negative	Same

| AUC _{last} | AUC to the Last Measurable Concentration |
| $\mathrm{AUC}_{0\text{-}\infty}$ | AUC Extrapolated to Infinity |
| $\mathrm{AUC}_{	au}$ | AUC of Dosing Interval |
| BA | Bioavailability |
| BE | Bioequivalence |
| BMI | Body Mass Index |
| BQL | Below the Quantification Limit |
| C_{last} | Last measurable concentration (above the quantification limit) |
| CL | Clearance |
| CL/F | Apparent Oral Clearance |
| C_{max} | Maximum Concentration |
| C_{trough} | Pre-dose Trough Concentration |
| CSR | Clinical Study Report |
| CV | Coefficient of Variation |
| F | Bioavailability |
| FDA | Food and Drug Administration |
| GM | Geometric Mean |
| hr | Hour |
| λ_{z} | Terminal Phase Elimination Rate Constant |
| LC/MS/MS | Liquid Chromatography-tandem Mass Spectrometry |
| LOD | Limit of Detection |
| LLOQ | Lower Limit of Quantification |
| Max | Maximum |
| Min | Minimum |
| NCA | Noncompartmental Analysis |
| PD | Pharmacodynamic |
| PK | Pharmacokinetic |
| AR | Accumulation Ratio |
| SD | Standard Deviation |
| SS | Steady State |
| τ | Length of the Dosing Interval |
| t _{1/2} | Apparent Terminal Elimination Half-Life |
| T_{last} | Time of Last Measurable Concentration |
| T_{max} | Time to Obtain Maximum Concentration (C _{max}) |
| V _d /F | Apparent Volume of Distribution |

1. PREFACE

DMID Protocol 16-0005 is a Phase I study of oxfendazole in healthy adult volunteers. The pharmacokinetic (PK)-related objectives of the study are:

- To define the multi-dose pharmacokinetics of oxfendazole
- To determine the effect of food on the pharmacokinetics of oxfendazole

This document reiterates key PK elements in the study design of 16-0005 and thoroughly describes the presentations and summaries of PK data as well as the noncompartmental analysis (NCA) to be included in a PK Report or in the clinical study report (CSR). Shells and mockups are given for all tables, figures, and listings planned for inclusion in the report.

Any deviation from this statistical plan will be described and justified in protocol amendments and/or in the report, as appropriate. The reader of this SAP is encouraged to also review the clinical protocol for details on conduct of the study and the operational aspects of clinical assessments.

Some minor modifications may be necessary to the planned design of tables, figures, and listings to accommodate data collected during the actual study conduct.

2. CLINICAL STUDY METHODS

2.1. Treatment Groups

This Phase I study is an open label multiple ascending dose evaluation of the safety and PK of oxfendazole (3, 7.5, or 15 mg/kg) in healthy adult men and nonpregnant women aged 18-45 (inclusive) followed by a single dose crossover trial evaluating the safety and pharmacokinetics of a single dose of oxfendazole (3 mg/kg) given following an 8 hour fast or following a high fat meal.

In the multiple ascending dose trial, each dose group will be comprised of 8 subjects, all of whom will receive study product once daily for 5 days. To enhance safety, 1 sentinel subject will be enrolled and followed for 7 days for defined safety events. A second sentinel subject will then be enrolled and followed for 7 days. If no predefined safety events are identified, the remaining 6 subjects in this group will be enrolled. All volunteers will be followed for 10 days and PK, safety laboratory and EKG studies will be performed. If no predefined safety events occur after all 8 subjects have completed the Day 10 visit, the DMID Medical Monitor will issue approval to proceed with enrollment of the second group of 8 subjects, who will receive 5 days of 7.5 mg/kg of oxfendazole using the same enrollment plan as outlined above. If no predefined safety events are encountered, the third group of 8 subjects will be enrolled to receive 5 days of 15 mg/kg using the same enrollment plan.

In the second phase of the study evaluating the effects of food on drug absorption, 12 subjects will be enrolled into a randomized, single dose, two-period, two-treatment (2x2) crossover trial. In the first period of this trial, half of the subjects will initially receive a single dose of 3 mg/kg of oxfendazole following an 8 hour fast, and the other half will receive a single dose of 3 mg/kg of oxfendazole following a high fat breakfast. After a one-week wash-out period, subjects will cross over in the second period to receive a single dose following a high fat breakfast or 8 hour fast. The order of conditions, Sequence A (fasted condition first) and Sequence B (fed condition first), will be randomly assigned upon enrollment in a 1:1 ratio.

Subjects who withdraw, or are withdrawn or terminated from the study, or are lost to follow-up after signing the informed consent form, randomization, and receipt of 3 or more doses of study drug will not be replaced. If the subject has only received two or fewer doses of study drug prior to termination from the study, the subject will be replaced. If a subject vomits more than two doses (i.e. if vomiting occurs within 1 hour of study drug administration and the subject vomits on two days or more), the subject will be replaced. Additionally, if the subject vomits within 1 hour after the receipt of the dose on day 1, the subject will be replaced. No more than two subjects will be replaced in any group. Unless prohibited by the volunteer, data and samples obtained prior to withdrawal will be included in study analysis. Subjects who withdraw, or are withdrawn or terminated from the study, or are lost to follow-up after signing the informed consent form and enrollment but before receipt of study product may be replaced. If a subject in

Group 4 is lost to follow up after the first dose, a replacement subject will be enrolled and randomized.

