4	12	3 mg/kg	Days 1 and 8 Dose received following a fast (n=6) or high fat meal (n=6) on Day 1 and crossed over to opposite arm to receive drug following high fat meal or fast on Day 8

Estimated Time to Complete Enrollment:

12 months

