5.3 Treatment Assignment Procedures

5.3.1 Enrollment and Randomization Procedures

Per International Conference on Harmonisation (ICH) guideline E6: Good Clinical Practice (GCP), screening records will be kept at the participating site to document the reason why an individual was screened, but failed trial entry criteria. The reasons why individuals failed screening will be recorded in the SDCC's AdvantageEDCSM (Electronic Data Capture system).

Once consented, the subject will be enrolled by entry of demographic data and confirmation of eligibility for the trial. This is an open label study and subjects will be enrolled sequentially into groups 1, 2, 3 and 4 until each group has been completely enrolled. Enrollment of subjects will be done online using the enrollment module of AdvantageEDCSM. AdvantageEDCSM will generate a treatment number for each subject after the demographic and eligibility data have been entered into the system.

All participants in group 4 will receive oxfendazole in two conditions: after a high-fat breakfast and after fasting (separated by one week). The order of conditions will be randomly assigned upon enrollment in a 1:1 ratio. The randomization code will be prepared by statisticians at the SDCC and included in the enrollment module for the trial. When the subject is randomized and enrolled, AdvantageEDCSM will generate a treatment assignment number.

Instructions for use of the enrollment module are included in the AdvantageEDCSM User's Guide. Manual back-up procedures and instructions are provided for use in the event that the site temporarily loses access to the Internet or the online enrollment system is unavailable.

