5.4.2 Handling of Withdrawals

The primary reason for withdrawal from the study will be recorded on the Study Status data collection form. Subjects will be encouraged to complete the Early Termination Visit. The Early

Termination Visit procedures are listed in Section 7.8. Although subjects are free to withdraw at any time or may be withdrawn by the site principal investigator or appropriate sub-investigator at any time, subjects who receive study drug will be encouraged to remain in the study for follow-up safety assessments and collection of venous blood samples for safety testing. Every attempt will be made to follow all adverse events, including systemic reactions, serious adverse events, ongoing at the time of early withdrawal to resolution.

In the case of subjects who fail to appear for a follow-up safety assessment, extensive effort (i.e., three documented contact attempts via phone calls, e-mails, etc., made on separate occasions and followed by a certified letter) will be made to locate or recall them, or at least to determine their health status. These efforts will be documented in the subject's records.

Subjects who withdraw, or are withdrawn or terminated from the study, or are lost to follow-up after signing the informed consent form, randomization, and receipt of 3 or more doses of study drug will not be replaced. If the subject has only received two or fewer doses of study drug prior to termination from the study, the subject will be replaced. If a subject vomits more than two doses (i.e. if vomiting occurs within 1 hour of study drug administration and the subject vomits on two days or more), the subject will be replaced. Additionally, if the subject vomits within 1 hour after the receipt of the dose on day 1, the subject will be replaced. No more than two subjects will be replaced in any group. Unless prohibited by the volunteer, data and samples obtained prior to withdrawal will be included in study analysis. Subjects who withdraw, or are withdrawn or terminated from the study, or are lost to follow-up after signing the informed consent form and enrollment but before receipt of study product may be replaced. If a subject in Group 4 is lost to follow up after the first dose, the subject will be replaced.

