$$Var(X) = [exp(\sigma^2) - 1] exp(2\mu + \sigma^2)$$

The coefficient of variation can be written in terms of σ^2 as:

$$CV = \frac{\sqrt{Var(X)}}{E(X)} = \frac{\left[\sqrt{exp(\sigma^2) - 1}\right] \exp\left(\mu + \frac{\sigma^2}{2}\right)}{\exp\left(\mu + \frac{\sigma^2}{2}\right)} = \sqrt{exp(\sigma^2) - 1}$$

Thus, the intrasubject coefficient of variation can be estimated from the model on log-transformed data as:

$$\widehat{CV_W} = \sqrt{\exp(MSE) - 1}$$

where MSE is the residual mean squared error from the model. Results from the statistical analysis of food effect will be shown in Table 31.

Distributional assumptions and homoscedasticity will be assessed by residual plots and/or other graphical diagnostics. Alternative analyses will be considered if assumptions are violated.

Food effect on T_{max} will be assessed with the Wilcoxon signed-rank test procedure. The Hodges-Lehmann estimator (pseudomedian) for the difference in T_{max} between fed and fasted conditions will be reported, as well as the associated 90% confidence interval will be displayed in Table 32. Potential differences in T_{max} due to sequence effects will be explored graphically.

3.6. Comparison of Current Pharmacokinetic Results to Pharmacokinetic Results from Previous Studies

Not applicable.

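### Nothing ties a Group 4 replacement to the sequence of the subject replaced, so the planned 6/6 split can drift, at a small and cheaply avoidable cost in precision

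*SAP*

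**What the plan says.** SAP Section 2.1 describes the food-effect part as follows: "12 subjects will be enrolled into a randomized, single dose, two-period, two-treatment (2x2) crossover trial". The order of conditions "will be randomly assigned upon enrollment in a 1:1 ratio". The group table in the Protocol Summary gives the intended split: "Dose received following a fast (n=6) or high fat meal (n=6) on Day 1".

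On the list itself, Protocol Section 5.3.1 says only this: "The randomization code will be prepared by statisticians at the SDCC and included in the enrollment module for the trial". Neither document mentions blocking, a forced 6/6 split or reserved replacement codes.

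On replacement, Protocol Section 5.4.2 reads: "If a subject in Group 4 is lost to follow up after the first dose, the subject will be replaced". It does not address sequence. SAP Section 2.1 covers the same event and adds how it is handled: "a replacement subject will be enrolled and randomized". Both documents also list other replacement triggers (termination after two or fewer doses, vomiting soon after the Day 1 dose, withdrawal before dosing). None of these has a sequence rule. The SAP sets a ceiling: "No more than two subjects will be replaced in any group".

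In SAP Section 3.5.7, AUC and Cmax are analysed with a mixed model containing period, condition and their interaction. Tmax is handled differently: "Food effect on T_{max} will be assessed with the Wilcoxon signed-rank test procedure".

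**The concern.** In a 2x2 crossover, the fed/fasted contrast is estimated most precisely when the sequences are equal in size. A replacement placed in the other sequence unbalances the completers although the total stays at 12. The protocol claims 80% power only for a CV below 0.175, so there is no reserve to absorb an avoidable loss.

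Balance also matters for outputs that do not adjust for period. A signed-rank test on fed-minus-fasted Tmax differences cancels a period shift only when the two sequences are equally represented.

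**Working it through.** **Inputs.** N = 12, planned 6/6 (Protocol Summary; SAP 2.1). 90% confidence interval with limits 0.80 to 1.25 (Protocol 11.1; SAP 3.5.7). Stated power of 80% for a CV below 0.175 and 64% at CV 0.2 (Protocol 11.2). At most two replacements per group (SAP 2.1). Assumed, because not stated: a true ratio of 1.00, a 6/6 start, and independent 1:1 draws for replacements.

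**Formula.** With σ_w = √ln(1 + CV²), the contrast has SE = σ_w·√[½(1/n_A + 1/n_B)] on n_A + n_B − 2 = 10 degrees of freedom. Power is the probability that the estimate ± t(0.95; 10)·SE lies within ±ln 1.25, averaged over the distribution of the estimated residual SD.

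**Reproducing the plan.** σ_w is 0.1737 at CV 0.175 and 0.1980 at CV 0.20. At 6/6 the SEs are 0.0709 and 0.0809, and power is 79.9% and 64.4%. Exactly 80% is reached at CV 0.1749. A true ratio of 0.95 would give 70.3% and 56.6%, so the protocol's figures imply a ratio of 1.00.

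**Unequal splits.** The variance ratio against 6/6 is (1/n_A + 1/n_B)/(1/6 + 1/6).

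| Completers | Variance ratio | SE increase | Power, CV 0.175 | Power, CV 0.20 |
|---|---|---|---|---|
| 6/6 | 1.000 | – | 79.9% | 64.4% |
| 7/5 | 1.029 | 1.4% | 78.5% | 62.6% |
| 8/4 | 1.125 | 6.1% | 73.5% | 56.5% |

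The loss is 1.5 and 1.9 points at 7/5, and 6.5 and 7.9 points at 8/4. Simulation with 200,000 trials per split agrees: 78.6% and 62.6% at 7/5, 73.3% and 56.7% at 8/4. At a true ratio of 0.95 the losses are similar: 1.4 to 1.6 points at 7/5 and 5.9 to 6.8 at 8/4.

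**How often.**
- One replacement: 6/6 or 7/5 with probability ½ each. Expected power is 79.2% and 63.5%, a mean loss of 0.7 and 0.9 points.
- Two replacements: both dropouts come from one sequence with probability 2·C(6,2)/C(12,2) = 30/66 = 0.45. Both replacements then fall in the other sequence with probability ¼. So 8/4 has probability 0.45 × 0.25 ≈ 0.11. Expected power over all two-dropout cases is 78.5% and 62.6%, a mean loss of 1.5 and 1.8 points.

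**Tmax.** Let p be a shift from period 1 to period 2. The fed-minus-fasted difference contains +p in fasted-first subjects and −p in fed-first subjects, so the average difference carries p(n_A − n_B)/12. That is 0 at 6/6, 2p/12 = p/6 in size at 7/5, and 4p/12 = p/3 at 8/4. This is the mean shift; the signed-rank location estimate is affected in the same direction.

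**The case against.** **The list structure is unknown.** The SAP does not say that a replacement is an independent draw; it could take the next slot on a blocked list. Suppose two dropouts come from one sequence and the replacements take slots 13 and 14. The chance of 8/4 is then ¼ with independent draws, 1/6 with blocks of four, and 0 with blocks of two. Conversely, under simple randomisation 12 subjects split exactly 6/6 only C(12,6)/2¹² = 23% of the time, so replacement would not be the main source of imbalance. This stands: the probabilities above are conditional on the assumed draw. The gap in the rule remains either way, because neither kind of list returns the replacement to the vacated sequence.

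**Replacing is still worthwhile.** Without replacement, power is 73.8% and 57.0% at 6/5, and 64.6% and 47.1% at 6/4. Replacement recovers most of that loss whichever sequence is assigned. This also stands; the issue is only how the sequence is chosen.

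**Stronger readings the documents do not support.** A reader might infer that the food-effect equivalence analysis becomes biased. It does not, because the AUC and Cmax model contains period. A reader might also infer that Tmax will be biased. That needs a period effect, and none is shown to be expected. The nominal washout is 168 h against a half-life of 8.5 to 11 h in the earlier single-dose study, which is at least 168/11 ≈ 15 half-lives, so carryover is unlikely. The SAP plans a graphical look at sequence differences in Tmax, and Tmax is not tested for equivalence. Finally, a reader might say that randomising the replacement has no benefit. It does keep the order unpredictable at enrolment, though that is worth little in an open-label, within-subject PK comparison.

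**Conclusion.** This is a low-cost improvement, not a flaw in the main analysis. As written, the replacement rule lets completers drift from 6/6 to 7/5, or at worst 8/4. The typical cost is about 1 to 2 points of power. It reaches 6.5 to 7.9 points only at 8/4, which is about 11% of two-dropout cases and impossible with one replacement. For AUC and Cmax the effect is on precision alone; for Tmax it is exposure to 1/6 or 1/3 of a period effect, if there is one.

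These figures assume a true ratio of 1.00, a 6/6 start, independent 1:1 replacement draws, and a count of completers only. No dropout rate is stated, so the overall chance of needing a replacement cannot be given.

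**What to change.** In SAP 2.1 and Protocol 5.4.2, state that a Group 4 replacement, for every replacement trigger listed, is assigned the same sequence as the subject replaced, through a replacement code issued by the SDCC. It would help to say in Protocol 5.3.1 whether the list forces 6/6, since the rule preserves whatever split was first allocated.

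The cost is a sentence in each document and a setting in the enrolment module, with no extra subjects or procedures. The replacement's order becomes predictable, which matters little here.

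The change balances paired completers only. Data from dropouts stay in the analysis, so the by-condition summaries can remain slightly uneven. Exclusion of AUC(0-∞) values with more than 25% extrapolation (SAP 3.4) can still unbalance that one parameter.

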2.2. Dose Administration

In the first phase of the study, subjects will be administered oxfendazole q24 hours via oral syringe by a study nurse or investigator on Days 1, 2, 3, 4 and 5. Subjects will be fasting (water is permitted) for 8 hours prior to, and for 2 hours after, the administration of drug

In the second phase, half of the subjects will receive a single dose of 3 mg/kg of oxfendazole following an 8 hour fast and the other half will receive a single dose following a high fat meal. After 7 days, each subject will cross over to receive a single dose of oxfendazole (3mg/kg) following either a high fat meal or following an 8 hour fast. Subjects receiving a high fat meal will be administered study product approximately 30 minutes (+/- 15 minutes) following completion of the meal. Subjects who fasted prior to receiving study product will remain fasting for 2 hours after administration of drug. Lunch and dinner will be provided. Subjects will be allowed to eat snacks but will be asked to avoid drinking grapefruit juice and excessive (>2 cups) coffee.

Subjects in both phases of the study will be provided lunch and dinner on day of dosing. If vomiting occurs following ingestion of the study product, that dose will not be replaced. All subjects will be counseled to avoid drug, alcohol, and tobacco use through the end of the study.

Additional details regarding study product administration can be found in the protocol and Manual of Procedures (MOP).

2.3. PK Sampling Schedule Treatment Groups

For the first phase of the study (Groups 1-3), 10 mL of blood for oxfendazole level will be drawn pre-dose and at 30 minutes, 1, 2, 3, 4, 6, 9, and 12 hours following the first dose. All times have a window of +/- 15 minutes except the 9 and 12 hour samples which have a window of +/- 30 minutes. On Days 2, 3, and 4, blood will be sampled for oxfendazole level approximately 24 hours (+/- 4 hours for Day 2, +/- 2 hours for Days 3 and 4) after the prior dose, but before the current study day dose. On Days 2, 3, and 4, approximately 2 hours (+/- 20 minutes) after administration of study drug, blood will be drawn for oxfendazole level. On Day 5, blood will be sampled pre-dose (24 hours +/- 2 hours after the prior dose) and at 30 minutes, 1, 2, 3, 4, 6, 9, and 12 hours (all times have a window of +/- 15 minutes except the 9 and 12 hour samples which have a window of +/- 30 minutes). Blood will also be sampled for oxfendazole level on Day 6, approximately 24 hours after dosing on Day 5 (+/- 6 hours) and Days 8 (+/- 1 day) and 10 (+/- 2 days).

In the second phase of the study (Group 4), blood sampling for oxfendazole level will be performed pre-dose and at 30 minutes, 1, 2, 3, 4, 5, 9, 12 and 24 hours following each dose on Day 1 and Day 8 (+/- 1 day). All times have a window of +/- 15 minutes except the 9 and 12

hour samples which have a window of \pm 0 minutes and the 24-hour sample which has a window of \pm 4 hours. Blood will also be sampled for oxfendazole level on Day 14 (\pm 0 days).

The exact time for all blood draws for oxfendazole level will be recorded and used for pharmacokinetic noncompartmental analysis (NCA).

